Surveys/EMAs. Questions assess immediate needs and trends over time. Partners will be asked about their own status and their perspectives on the patient's status. Advice or referrals to other A-CHESS or PartnerCHESS services will arise from responses to questions as well as from the Bayesian prediction of relapse risk using data from discussion groups and surveys.⁴¹

Guided relaxation. Audio to guide mindfulness, relaxation exercises, games, and other help for cravings.

Meeting locator. Patients and partners can use GPS to find AA/AI Anon meetings. Smartphone GPS data enable clinicians to estimate treatment adherence, e.g., attending 12-step meetings or other appointments.

Healthy activities. Database of ideas (e.g., taking a walk) and local recovery-friendly activities. Couples can add them to their recovery calendar.

Crisis button. Relaxation exercises, optional calls to supporters, games for distraction, and other resources.

Skills reminders. Tips and reminders of CBT-based skills (e.g., effective communication, refusal skills, etc.)

6-month pilot PartnerCHESS services from ABCT. Patients randomized to the PartnerCHESS group will receive all A-CHESS services listed above, plus the following services from ABCT:

Urge discussion. Daily EMAs will track preconditions for relapse (urges), review urge reduction options on PartnerCHESS, and encourage discussions between partners on the causes of and ways to reduce urges.

[figure not shown]
Homework checklist. Tracks which interventions the couple is using/practicing, along with resources to help.

Relapse plan. Monitoring and reminders of steps planned for relapse prevention.

Reminders. Reminders to notice something positive in partner, of reasons to stay sober, to take meds, etc.

Trigger identification and removal. During set-up, patient and partner enter triggers. PartnerCHESS will quiz couples on upcoming trigger events and remind them of ways to address each.

Conceptual model of study. Figure 1 shows the conceptual model we propose to study. It suggests that PartnerCHESS and A-CHESS will improve the secondary outcomes both directly and through

multiple meditational paths. Changes in secondary outcomes (e.g., sleep⁵⁸) will improve the primary outcomes. We anticipate that PartnerCHESS will (more than A-CHESS alone) affect the patient's intrinsic motivation to abstain as well as his or her relatedness

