Mediator effects are statistically significant if: (a) the beta-weight coefficients in Steps 1 and 2 differ significantly from zero, (b) the Step 3 beta-weight coefficient of the mediators is statistically significant, and, (c) the difference between the beta-weight coefficients of the intervention variable in Steps 1 and 3 is statistically greater than zero. We will test whether patient and partner gender moderates the effect of intervention on outcomes. We will derive interaction terms for the predictor variables, incorporating them into the regression model, and determine whether those terms significantly contribute to the outcome predictions that exist independent of other significant contributors. We will examine moderated mediation because the process may be more complex than can be rendered by treating the factors independently (e.g., a mediator may be stronger for women than men or vice versa). We will develop a moderated mediation structure to determine whether the results are best described by meaningful higher-order interaction terms based on mediator-moderator combinations.

Power. We understand that estimating effect size from pilots can lead to bad estimates. A paper by Leon, Davis, and Kraemer² points out that a pilot study can evaluate the. It informs feasibility and identifies modifications needed before a larger hypothesis-testing study. But (they argue) a pilot study does not provide meaningful effect size estimates for planning subsequent studies because of the imprecision inherent small samples. Rather, a hypothesis-testing study should be designed to detect the smallest difference that is generally agreed to be clinically meaningful. Several studies (e.g. Walters et al.)³ suggest that an effect size of $d=.35$

is considered clinically meaningful. So we will use $d=.35$ at a power of .85 to determine sample size needed for the large study.

This particular pilot is not powered to detect any effect on outcomes. Once the R34 analyses are complete, we will develop the R01 proposal based on the previous work mentioned above but also considering what we learn about the feasibility of recruitment, randomization, retention, assessment procedures, and new methods mentioned above.

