Missing data. In previous RCTs, we completed about 85% of surveys through 12 months and kept missing data on core survey items to about 2%. We expect these rates in this study. In addiction treatment, data are not likely to be missing at random (i.e., the probability that data are missing relates to what the data would have been had they been observed). For example, a patient may not want to disclose some information in surveys. Because this may lead to biased parameter estimates, we will identify missing data patterns and use pattern-mixture modeling to test the sensitivity of our analysis to missing data assumptions⁹¹⁻⁹⁴ and conduct other sensitivity analyses after imputing missing data with a range of plausible values based on assumptions for the missing data (e.g., best-case, worst-case; with and without multiple imputation).⁹⁵⁻⁹⁷

Intention-to-treat and subject noncompliance. Standard intention-to-treat (ITT) estimates the average treatment effect by comparing outcomes based on assignment of the treatment, but ignoring use of the treatment. Because ITT effect estimates do not represent treatment efficacy under noncompliance (e.g., a patient is randomized to PartnerCHESS but does not use the system), we will estimate noncompliance by also estimating treatment effects only for compliers using As-treated, Per-Protocol⁹⁸ and CACE.⁹⁹

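### As-treated and per-protocol comparisons are labelled as effects among compliers; of the three methods listed only CACE targets that effect, and the other two are open to selection bias of unknown direction

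*Combined protocol and SAP*

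**What the plan says.** The paragraph on intention-to-treat and noncompliance in section 8.0 describes ITT and then gives the reason for going further: "Because ITT effect estimates do not represent treatment efficacy under noncompliance". The added analyses are described as "estimating treatment effects only for compliers using As-treated, Per-Protocol", and the same sentence goes on to name CACE. All three are therefore given one purpose.

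The only description of noncompliance is an example: "a patient is randomized to PartnerCHESS but does not use the system". The paragraph sets no use threshold, no expected use rate, no rule for A-CHESS patients or for partners, no adjustment for self-selected use, and no CACE assumptions.

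Other sections bear on this:

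- Section 5.0 says PartnerCHESS patients "will receive all A-CHESS services listed above, plus the following services from ABCT". Both arms therefore have an app, and one is a superset of the other.
- Section 7.0 gives PartnerCHESS partners access and gives A-CHESS partners neither app.
- The Power paragraph of section 8.0 adopts d = 0.35 "at a power of .85 to determine sample size needed for the large study", and says of the present trial: "This particular pilot is not powered to detect any effect on outcomes".
- The project summary and section 2.0 nevertheless list effect-size estimation among the pilot's purposes.

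**The concern.** A complier is defined by what a patient would do if assigned to the intervention. CACE uses the randomized contrast and scales it by the share who comply. As-treated regroups patients by the use they actually made and is not restricted to compliers. Per-protocol keeps selected subsets of each arm. If use is related to prognosis, both differ from zero even when the intervention does nothing.

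The documents give reason to expect such a relation. Section 5.0 expects use of some services to vary with sex, and section 8.0 lists use as a moderator. The couple-oriented services may also select different patients from those who use A-CHESS alone.

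What is at stake is interpretation. The paragraph presents these estimates as addressing efficacy where ITT does not. A reader of the pilot report could take a confounded comparison for the effect in those who used the app.

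**Working it through.** **Stated figure.** Section 5.0 expects about 10% dropout from 34 dyads randomized 1:1. 17 × 0.90 = 15.3, which agrees with its figure of about 15 per arm. The documents give no figure for compliance or bias, so what follows rests on assumed inputs.

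**Model, true effect zero for everyone.** Let U be propensity to use the app, standard normal. A patient is a user if U exceeds a cut-off k, with share of users c. The outcome Y has SD 1, is scored so that higher is better, and has correlation ρ with U. Let φ be the normal density at k. Then E[U | user] = φ/c and E[U | non-user] = −φ/(1−c).

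**As-treated.** The plan gives no rule for PartnerCHESS non-users, who receive neither app. I assume they are pooled with the whole A-CHESS arm, whose mean is 0. The pooled mean of U is −φ/(2−c), so

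bias = ρ × [φ/c + φ/(2−c)] = ρ × 2φ / [c(2−c)].

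| PartnerCHESS use c | φ | multiplier of ρ | bias, ρ = 0.3 to 0.5 | ρ needed for 0.35 |
|---|---|---|---|---|
| 50% | 0.399 | 1.064 | 0.32 to 0.53 | 0.33 |
| 60% | 0.386 | 0.920 | 0.28 to 0.46 | 0.38 |
| 70% | 0.348 | 0.764 | 0.23 to 0.38 | 0.46 |
| 80% | 0.280 | 0.583 | 0.18 to 0.29 | 0.60 |
| 90% | 0.175 | 0.354 | 0.11 to 0.18 | 0.99 |

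The bias is proportional to ρ, so its sign follows ρ. At c = 60% and ρ = −0.3 it is −0.28.

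**Per-protocol, non-users excluded in both arms.** Bias = ρ × (E[U | PartnerCHESS user] − E[U | A-CHESS user]). At 60% versus 80% use this is ρ × (0.644 − 0.350) = 0.294ρ, or 0.09 to 0.15 SD. Reaching 0.35 would need ρ = 0.35/0.294 = 1.19, which is impossible. With the same share and kind of patient excluded in each arm, the bias is 0.

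**Per-protocol, non-users excluded in the PartnerCHESS arm only.** Bias = ρφ/c, which is (2−c)/2 times the as-treated bias. At 60% use it is 0.644ρ, or 0.19 to 0.32; at 50% it is 0.798ρ, or 0.24 to 0.40. The plan does not say which exclusion it intends.

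**CACE.** With use of PartnerCHESS possible in one arm only, CACE = ITT/c. Its large-sample bias is 0 under randomization and the exclusion restriction, meaning that assignment affects the outcome only through compliance. Precision is poor. The standard error of ITT is √(2/17) = 0.34 at 17 per arm and √(2/15) = 0.37 at 15. Dividing by c = 0.6 gives about 0.57 to 0.61.

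**Simulation, 17 per arm, 60% versus 80% use, ρ = 0.3 to 0.5, true effect zero:**

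| Estimate | share of null trials at or above 0.35 |
|---|---|
| ITT | 15% to 16% |
| As-treated | 42% to 62% |
| Per-protocol (both arms) | 26% to 30% |
| CACE (SD about 0.62) | about 27% |

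**The case against.** The strongest reply is that this is a supplementary analysis in a pilot that disclaims power. ITT is retained and CACE is already listed. The Power paragraph says that pilots do not yield useful effect sizes for planning, and uses d = 0.35 to size the later study. All of that stands. A reader might infer that d = 0.35 is a target of this trial, or that the R01 decision turns on these two estimates. The documents support neither reading.

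A reader might also infer that the bias must flatter PartnerCHESS because motivated patients use the app more and drink less. The documents do not say so. Section 5.0 describes crisis and craving tools and staff calls prompted by worrying trends, so patients in difficulty could be the heavier users. Nor do the documents establish that use will be lower in PartnerCHESS; its daily prompts could raise it.

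A third tempting step is to treat CACE as a clean repair if compliance is defined as the patient's use of the added ABCT services. It is not. A non-complying patient's partner still has the app, whereas A-CHESS partners have none, and the conceptual model in section 5.0 expects partner effects to reach the patient. At this sample size CACE also exceeds 0.35 by chance about as often as per-protocol does. Its advantage is that it has the right target, not that it protects a small trial from chance.

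What the reply does not answer is the label. Low power does not turn a confounded comparison into a complier effect, and effect-size estimation remains among the pilot's stated purposes.

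**Conclusion.** The point holds as a labelling error together with a missing compliance definition. As-treated and per-protocol do not estimate the effect the plan assigns to them; CACE does, subject to its assumptions.

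The size is conditional on use rates, correlations and pooling rules that the documents do not give. Over the assumed ranges, as-treated bias is 0.18 to 0.53 SD. It matches 0.35 only at correlations from about 0.33 (50% use) to 0.60 (80% use), and at 90% use it stays below 0.2 for correlations up to 0.5. Per-protocol with exclusion in both arms gives 0.09 to 0.15 SD in the scenario shown and can be zero. The broad claim that both methods can produce an apparent effect as large as d = 0.35 is therefore not supported: it rests mainly on as-treated. Per-protocol gets there only with one-arm exclusion, low use and a correlation near the top of the range, or with a much wider gap in use between arms. The direction is unknown throughout.

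**What to change.** Revise the noncompliance paragraph in section 8.0:

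1. Keep ITT as the main estimate, as already planned.
2. Name CACE as the only estimate of the effect among compliers. Report it with its interval and its assumptions, and note that it is very imprecise at about 15 to 17 dyads per arm.
3. Define compliance at dyad level, with a stated threshold, counting the partner's app use as well as the patient's use of the added ABCT services. Acknowledge that the exclusion restriction may still not hold fully, because partner access alone could affect the patient.
4. Relabel as-treated and per-protocol as descriptive associations between use and outcome, state how non-users in each arm are classified, and say that these results are not treatment effects and are not a basis for the R01 decision.

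The cost is a few lines of text, with no change to data collection, since app use is already recorded automatically. The downside is that two customary estimates are no longer reported as effects.

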9.0 COI MANAGEMENT PLAN REQUIREMENTS

In accordance with [name] of Interest Management Plan [name] will be responsible for acting as an independent reviewer of the analysis. [name] is a professor in the Department of Communication Arts at the University of Wisconsin and has 30 years of experience working as a PI performing data analysis.

10.0 RECORDS TO BE KEPT

The following records will be kept during the course of the study.

- Subject Intake
- Subject Demographics
- Subject Consent Forms
- HIPAA Authorization Form
- Baseline and follow up survey data
- De-identified A-CHESS and PartnerCHESS use data collected during this study

11.0 DATA SECURITY AND PRIVACY MONITORING PLAN

In accordance with the Health Insurance Portability and Accountability Act (HIPAA) the following Data Security and Privacy Monitoring Plan has been established at the Center.

I. Appointment of Center Data Security Officers.

- A. [name], [name] and [name] are the security officers for the Center.
- B. Responsibilities of the security officers include:
 - Developing information technology (IT) security policies
 - Increasing security awareness and providing training for all Center faculty and Team Members
 - Providing virus protection for IT resources
 - Maintaining security patches on computing equipment
 - Developing and implementing back up procedures
 - Performing periodic vulnerability scanning on computers
 - Reviewing and updating firewall strategies and policies
 - Enhancing the physical security of IT resources
 - Annual review of staff policies and procedures contained in this document.
 - Conduct formal HIPAA Risk Assessment Inventory per requirements of the UW HIPAA Office; last review completed summer 2012.

II. Policy for Orientation and Training

- A. All Center students, faculty and staff are required to complete the UW-Madison Human Subjects training on-line at <https://my.gradsch.wisc.edu/citi/index.php>. You register with your NetID. Select the training for the **UW Social & Behavioral Course**. Please print out your certificate of completion when you have finished, and give it to [name]. You will need to take a refresher course every three years.
- B. Successful completion of the CITI training is required before any Team Member is allowed access to Center data.
- C. All Center Team Members are also required to complete an on-line training course on the HIPAA Privacy Rule which is offered through Learn@UW at <https://learnuw.wisc.edu/>. You will only need to complete the **HIPAA Privacy and Research at UW** course. Contact [name] if you do not have the HIPAA training on your Learn@UW dashboard. Please print out your certificate of completion when you have finished, and give it to [name]. You will need to retake this course annually.
- D. Successful completion of the HIPAA training is required before any Team Member is allowed access to Center data.
- E. All Center Team Members are required to complete training with [name] on Center security procedures and policies.
- F. Sign (on the last page) the “Center Data Security Policy and Privacy Monitoring Plan” upon completion of this training and return to [name].

III. Workstation Policy

- A. All workstations will require login with a unique user name and password.
- B. All workstations are required to be joined to the ENGR domain under the control of the College of Engineering. Access to specific folders on the Center network will be approved by the Center Management team or the study Project Director.
- C. All workstations are required to use anti-virus software that can be remotely administered from the College of Engineering domain.
- D. Users will log-out from or lock workstations when leaving them unattended.

- E. Screen savers will be configured to require a password and to activate after ten minutes of workstation inactivity.
- F. Users requiring remote access to the Center network will only do so with computers specifically certified by a Center Data Security Officer.
- G. Study coordinators or support personnel using desktops in private or public areas must have screens adjusted so that visitors cannot read the screen upon entering the space in case PHI or other confidential information is displayed.
- H. Access to the network or center work stations along with any on-line systems will be terminated immediately following an employee's last day of work at the Center.

IV. Password Policy

- A. Users will require a password to access any computer connecting to the Center network.
- B. Passwords must meet the requirements of the Computer Aided Engineering department (CAE). CAE password construction help can be found here: <https://kb.wisc.edu/cae/page.php?id=8143>.
- C. Ideally the best practice is to re-set your password on a semi-annual basis.
- D. Passwords may not be stored in proximity to the workstation and may not be shared by others.

V. Policy for the Use of Email

- A. Patient Identifiable, Confidential, or Personnel Data may only be included in an encrypted attachment and should never be sent in the body or subject line of an email message.
- B. Team Members who need to send encrypted attachments should contact a Center Data Security Officer to schedule a training session.

VI. Policy for Storage, Retrieval, and Disposal of Protected Information

- A. Effective 1/1/14 any new studies must use the REDCap environment for study participant information. Contact [name] for start-up and access information.
- B. Any Patient Identifiable, Confidential, or Personnel Data in electronic form will be stored on secure servers only and **may not** be stored on individual workstations, laptops, or any other endpoint devices. Currently, the only place such information can be stored is the R: Drive for studies prior to 1/1/14 or REDCap.
- C. Study coordinators will have printers in their office for printing any materials that include PHI and/or names of study participants.
- D. All paper-based files will be stored in locked rooms inside locked file cabinets with limited access.
- E. Any offices that contain PHI must be locked when leaving a room.
- F. Servers containing Patient Identifiable, Confidential or Personnel Data must be located within physically secured server rooms which can only be accessed by authorized personnel.
- G. The Center Data Security Officers will be responsible for assigning and restricting access to shared resources on Center servers.
- H. Patient Identifiable, Confidential, and Personnel Data as a general rule may not be copied to or stored on the Center's publicly accessible servers at any time. However, in some studies, patient's name, disease state, and physician are stored within Center applications only accessible via a secure connection using a codename/password.

- I. Remote access to files on secure Center servers will be provided in a very limited case only through a connection from a certified Center Workstation (see Center Workstation policy above for details).
- J. Storage media containing Patient Identifiable, Confidential or Personnel Data will be rendered unusable before disposal.
- K. All back up media will be stored in locked rooms with limited access.

VII. Policy for the use of endpoints (e.g. workstation smartphone, laptop, thumb drive, external hard drive, etc.) accessing Patient Identifiable, Confidential, and Personnel Data

- A. Staff are not allowed to access or store any PHI data on any endpoint unless the endpoint is provided by a Center Data Security Officer ensuring that the endpoint is protected and secured. In addition, any PHI data residing on an endpoint must also be encrypted with the oversight of a Center Data Security Officer.
- B. All endpoints accessing PHI must be owned and provisioned by the Center.
- C. Patient Identifiable, Confidential, and Personnel Data files may not be transported from the Center unless the device/medium is monitored for physical security at all times and the data is encrypted on the mobile device.
- D. Remote access to any PHI data must be conducted using a secure and encrypted end-to-end connection implementing modern security best practices either over HTTPS or using the WiscVPN connection.

VIII. Policy governing the storage and use of audiovisual materials

- A. Audiovisual media containing Patient Identifiable, Confidential, and Personnel Data are governed by the same policies and procedures that apply to handling and use of computerized data, including disposal, storage and access to media.
- B. Such audiovisual media may not be transported from the Center unless the material is monitored for physical security at all times.

IX. Policy governing the transmission of information via fax

- A. All outgoing correspondence via fax must be stripped of confidential information.
- B. Before confidential information is transmitted to the Center via fax, the sender must notify the appropriate Center Team Member to ensure that the recipient is available to pick up the fax document.

X. Field hardware policy

- A. Device provided for study participants will require log-in information to access the device.
- B. Upon their return, all Center study computers, smartphones, or other devices that have been used in the field will have all data wiped from the hard drive in compliance with DOD standards.
- C. Field computers will be stored at the Center in a wiped state.

XI. Study participant information.

- A. Center Team Members will not share or talk about confidential information regarding the CHESS study participant with anyone who is not directly involved in the management of the CHESS Project.
- B. Confidential or other sensitive information regarding the study participant cannot be left in an unsecured place where others may see it.
- C. Copies of written correspondence about the study participants with anyone other than CHESS management cannot be provided, unless specifically authorized to do so by the Project Director.
- D. Access to study participant's PHI will be approved by the Project Director in coordination with the PI for the project. As noted in Section VI, studies beginning after 1/1/14 must use REDCap to enter participant information electronically.

XII. User Responsibilities

- A. All Center Team Members are responsible for adhering to the Center Data Security and Privacy Monitoring Plan Policies at all times. In addition, all Center Team Members are responsible for adhering to the UW-Madison IT policies detailed at <https://it.wisc.edu/about/office-of-the-cio/it-policies/> at all times as well.
- B. All Center Team Members will be given a comprehensive briefing session upon hire.
- C. Usernames and passwords are not to be shared with others.
- D. No equipment may be connected to the Center network without specific prior certification by a Center Security Officer.
- E. Specifically, no wireless access points may be deployed or connected to the network under any circumstances.
- F. The Center Data Security Officers will maintain records to insure that all Center Team Members have been briefed.
- G. The Center Data Security Officers will provide periodic refresher sessions to all Center Team Members.

XIII. Sanctions for non-compliance with Center data security and privacy policies

DEFINITION OF OFFENSE:

Class I offenses:

- (1) Accessing information that you do not need to know to do your job;
- (2) Sharing your computer access codes (user name & password);
- (3) Leaving your computer unattended while you are logged into a PHI program;
- (4) Sharing PHI with another employee without authorization;
- (5) Copying PHI without authorization;
- (6) Changing PHI without authorization;
- (7) Discussing confidential information in a public area or in an area where the public could overhear the conversation;
- (8) Discussing confidential information with an unauthorized person; or
- (9) Failure to cooperate with privacy officer.

Class II offenses:

- (1) Second offense of any class I offense (does not have to be the same offense);
- (2) Unauthorized use or disclosure of PHI;
- (3) Using another person's computer access codes (user name & password); or
- (4) Failure to comply with a resolution team resolution or recommendation.

Class III offenses:

- (1) Third offense of any class I offense (does not have to be the same offense);
- (2) Second offense of any class II offense (does not have to be the same offense);
- (3) Obtaining PHI under false pretenses; or
- (4) Using and/or disclosing PHI for commercial advantage, personal gain or malicious harm.

SANCTIONS:

Class I offenses shall include, but are not limited to:

- (a) Verbal reprimand;
- (b) Written reprimand in employee's personnel file;
- (c) Retraining on HIPAA Awareness;
- (d) Retraining on Center's Privacy and Security Policy and how it impacts the said employee and said employee's department; or
- (e) Retraining on the proper use of internal forms and HIPAA required forms.

Class II offenses shall include, but are not limited to:

- (a) Written reprimand in employee's personnel file;
- (b) Retraining on HIPAA Awareness;
- (c) Retraining on Center's Privacy and Security Policy and how it impacts the said employee and said employee's department;
- (d) Retraining on the proper use of internal forms and HIPAA required forms; or
- (e) Suspension of employee (In reference to suspension period: minimum of one (1) day/maximum of three (3) days).

Class III offenses shall include, but are not limited to:

- (a) Termination of employment;
- (b) Civil penalties as provided under HIPAA or other applicable Federal/State/Local law; or
- (c) Criminal penalties as provided under HIPAA or other applicable Federal/State/Local law.

XIV. In case of a PHI breach, Center Security Officer and/or PI reports incident to UW HIPAA Security Office who is responsible for adhering to breach notification standards.

Definition of Terms

Protected Health Information (“PHI”): Health information or health care payment information, including demographic information collected from an individual, which identifies the individual or can be used to identify the individual.

Confidential Information: Proprietary information such as algorithms built into CHESS technology tools, information about a study participant (e.g. name, address, diagnosis) and similar topics.

Personnel Information: Salary rates, disciplinary actions, layoff notices and similar topics about individuals working at the Center or the university.

REFERENCES

